CV	Coefficient of Variation			
EDC	Electronic Data Capture			
g	Gram(s)			
GM	Geometric Mean			
GSD	Geometric Standard Deviation			
h	Hour(s)			
Ke	Terminal Phase Elimination Rate Constant			
kg	Kilogram(s)			
L	Liter(s)			
LLOQ	Lower Limit of Quantification			
Max	Maximum			
Min	Minimum			
min	Minute(s)			
mL	Milliliter(s)			
NCA	Noncompartmental Analysis			
μg	Microgram(s)			
PK	Pharmacokinetic(s)			
SD	Standard Deviation			
t1/2	Apparent Terminal Elimination Half-Life			
Tlast	Time of Last Measurable Concentration			
Tmax	Time to Maximum Serum Concentration (Cmax)			
Vz	Apparent Volume of Distribution During Terminal Phase			

1. Introduction

This **pharmacokinetic** analysis plan describes the rules and conventions to be used in the presentation and analysis of PK data to be presented for Protocol [OBI-888-001]. This document is based on protocol, version 4.0, dated 07 Jun 2019.

This document reiterates key PK elements in the study design of Protocol OBI-888-001 and thoroughly describes the presentations and summaries of PK data as well as the noncompartmental analysis (NCA) to be included in the PK Report and summarized in the clinical study report (CSR) for this protocol. Shells and mockups are given for all PK-related tables, figures, and listings planned for inclusion in the CSR and/or PK Report. At minimum, mean PK plots as well as listings and summaries of OBI-888 concentrations and PK parameters will be included in the CSR, while all tables, figures, and listings described in this document will be included in the PK Report.

2. CLINICAL STUDY METHODS

2.1. Analysis Groups

This is a Phase I, open-label, dose-escalation (Part A) and cohort expansion (Part B) study of OBI-888, a humanized mAb targeting Globo H in patients with locally advanced or metastatic solid tumors. Part A is designed to establish the MTD and RP2D of OBI-888. Part B is intended to further characterize the safety and clinical activity profile of the RP2D dose of OBI-888 administered as monotherapy in patients with locally advanced or metastatic solid tumors.

2.2. Dose Administration

OBI-888 were administered as a 90-minute intravenous (IV) infusion on Days 1, 8, 15, and 22 of each 28-day cycle. The infusion duration may be reduced, at the investigator's discretion, to 30-60 minutes starting with Cycle 3 if the infusions in the first two cycles were well tolerated.

For Part A (Dose Escalation), OBI-888 will be given at the dose levels of 5, 10, and 20 mg/kg until MTD is determined. For Part B (Cohort Expansion), subjects were treated with 20 mg/kg OBI-888 since no DLTs have been observed at any dose level tested in Part A, and the MTD was not reached.

2.3. PK Sampling Schedule

Blood (serum) samples will be collected at the following time points: C1D1 Pre-infusion (within 1 day prior-to the infusion), post infusion samples at the end of infusion and at 1 (\pm 15 min), 4 (\pm 15 min), 8 (\pm 15 min), 24 (\pm 2 h, on Day2), 72 (\pm 2 h, on Day4) and 168 hours (any time prior to C1D2 infusion) after the end of the infusion.

Statistical Analysis Plan: OBI-888-001 Review Status: Final Version: 2.0

Version Date: 02JUN2022

2.4. Analytical Methods

The concentration of OBI-888 in the serum samples were determined using a validated ELISA method with an assay range of 468.75 to 30000 ng/mL.

3. PHARMACOKINETIC ANALYSIS METHODS

3.1. Analysis Population and Handling of Missing Time Points

The PK population will include all enrolled subjects who receive at least 1 dose of study drug and have sufficient PK samples (a sample at the end of administration and at least 3 samples during the elimination phase) to include in the PK assessments. Generally, only values above the lower limit of quantification (LLOQ) are used for the estimation of PK parameters. Unless otherwise specified below, missing sampling or concentration values should not be imputed, but left missing in the calculation of derived PK parameters. If the actual sampling time is missing, but a valid concentration value has been measured, the scheduled protocol time may be used for the calculation of derived PK parameters. Collection of serum samples outside of the protocol defined time window for the time point will not result in exclusion of the sample result from NCA. Values below the lower limit of quantification (LLOQ) will be referred to as below the quantification limit (BQL). BQL values that precede the first PK concentration above the LLOQ will be imputed as 0 for linear plots and for all calculations including NCA and summary statistics. All other BQL values will be treated as missing for all analyses.

3.2. Demographic and Baseline Characteristics

Sex, race, age, weight, height, and body mass index (BMI) of subjects in the PK analysis population will be listed and summarized (PK Table 1, PK Listing 1).

3.3. Dosing and Pharmacokinetic Sampling Summary

Subject dose administration times will be presented (PK Listing 2). Cases that potentially affect the analysis will be discussed. Protocol deviations related to dosing or PK sampling will be listed (PK Listing 3) and summarized in the PK Report text. Deviations to be included in the PK Report include:

- Blood specimen not collected
- Plasma specimen result not obtained
- Specimen temperature excursion
- Required specimen collected out of window
- Any other deviation determined by the PK analyst to be potentially affect PK

Drug plasma concentrations will be listed by subject (PK Listing 4), with nominal and actual time

associated with the sample indicated (nominal time is defined as the time in h since the start time of the dose). Both laboratory reported concentration values, and modified concentration values used for analysis (for instance, imputation of 0 for a BQL value at baseline) will be included, as separate columns, in the listing. Plasma drug concentrations will also be summarized (PK Table 2) and plotted. PK Figure 1 and PK Figure 2 will plot all individual subject plasma PK profiles, as linear and semi-logarithmic plots, respectively. Subject ID for each individual profile in these figures will be shown in a legend.

3.4. Definition and Estimation of Individual NCA PK Parameters

PK parameters will be estimated through a NCA using version 8.2 or later of Phoenix® WinNonlin® (Pharsight Corporation, Cary, NC). Actual post-dose time will be used for the estimation of PK parameters instead of nominal time. Individual PK parameter estimates will be listed (PK Listing 5).

Phoenix® WinNonlin® NCA will use the following settings to compute parameters from plasma PK data:

- Linear Up Log Down calculation method
- Uniform weighting
- Intravenous dose
- Plasma Model Type
- Lambda Z Acceptance Criteria
 - Rsq adjusted ≥ 0.80
 - Span ≥ 2.0 half-lives
 - Includes ≥ 3 timepoints after Tmax

 T_{max} (hour): Time to reach the maximum concentration

- directly taken from the observed concentration

 C_{max} (µg/mL): Maximum concentration

- directly taken from the observed concentration

C_{last} (µg/mL): Concentration at last quantifiable time point

Version: 2.0 Version Date: 02JUN2022

Review Status: Final

- directly taken from the observed concentration

 λ (1/h): Elimination rate constant associated with the terminal phase

- estimated terminal slope of the linear regression of log-transformed concentration vs time
- The regression analysis should contain data from at least 3 different time points in the terminal phase and as many data points as possible, always including the last quantifiable concentration but excluding the concentration at $T_{\rm max}$.
- The coefficient of determination Adj_RSq² should be larger than or equal to 0.80. If at least one of these three conditions is not fulfilled, the terminal half-life and the parameters depending on t½ will be listed but flagged as not reliably calculated. They will generally be excluded from descriptive statistics and statistical testing procedures.

t_{1/2} (h): Terminal elimination half-life

$$- t_{1/2} = \frac{\log_e 2}{\lambda}$$

AUC_{last} (h*µg/mL): Area under the concentration-time curve from time zero to time the last quantifiable time, calculated by log-linear trapezoidal rule.

 $AUC_{\infty}(h*\mu g/mL)$: Area under the concentration-time curve from time zero to infinite time

- The percentage of extrapolated AUC should not exceed 20% of AUC∞ for each individual profile. If the percentage of extrapolated AUC is more than 20%, the individual AUC∞ result and the parameters depending on AUC∞ will be listed but flagged as not reliably calculated. They will generally not be included in descriptive statistics and statistical testing procedures.

AUMC_{last} (h²*µg/mL): Area under the first moment of the concentration time curve from time zero to time the last quantifiable time, calculated by log-linear trapezoidal rule.

AUMC_∞ (h²*μg/mL): Area under the first moment of the concentration-time curve from time zero to infinite time

CL (mL/h): Total body clearance following iv administration

-
$$CL = \frac{Total\ Dose\ Administrated\ in\ "\mu g"}{AUC_{\infty}}$$

V_z (mL): Volume of distribution following iv administration

Statistical Analysis Plan: OBI-888-001 Review Status: Final Version: 2.0

Version Date: 02JUN2022

-
$$V_z = \frac{CL}{\lambda}$$

V_{ss} (mL): Volume of distribution at steady-state following iv administration

-
$$V_{SS} = \frac{Total\ Dose\ Administrated\ in\ "\mu g" \times AUMC}{(AUC_{\infty})^2}$$

Dose proportionality

- To investigate the dose proportionality of AUC and Cmax, a statistical analysis using the power model will be conducted. The power model will have the form:
- $Y = a*(dose)^b$, where Y is the PK parameter, and a and b are the coefficient and exponent, respectively, of the power equation.
- By taking the natural logarithm (ln), the power model can be analyzed using linear regression and has the form:
- $ln(Y) = ln(a) + b*ln(dose) + error = \alpha + \beta*ln(dose) + error$,
- where α is the intercept, and β is the slope, and ln(dose) is based on the dose size for each subject.
- Estimates of slope and intercept along with their 90% confidence intervals will be reported. A minimum of 3 values per dose must be available for a given parameter to estimate dose proportionality using the power model.

All calculations will use the actual post-dose times recorded on the CRF. All computed PK parameters will be listed by subject and summarized by dose group in the Escalation Phase and by disease cohort in the Expansion Phase (mean, standard deviation, coefficient of variation, minimum, maximum, number of observations). Individual and mean (by time) concentrations versus time will be plotted for each dose on both linear and natural logarithm scales.

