8.2.3 Duration of Infusion

OBI-888 investigational drug solution (OBI-888 drug product mixed with saline/glucose infusion solution) should be administered as IV infusion by the site staff.

The infusion should be given for a duration of approximately 90-minute (± 10 minutes), for the initial two cycles (C1 and C2).

The infusion duration from Cycle 3 could be reduced, if no infusion related AEs to prior infusions occur, to 30 minutes or 60 minutes at the discretion of the Investigator.

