14.4 Pharmacokinetic Analysis

PK parameters will be calculated using a non-compartmental method from the PK samples collected on Dose 1 and will include C_{max} , total exposure (AUC), $t_{1/2}$, Cl, T_{max} , and V_d . To assess the attainment of steady state, trough (C_{min}) concentrations and peak concentrations (end of infusion) of each dose would be obtained directly from analytical data.

Summary statistics will be tabulated for the PK parameters of OBI-888 on Dose 1. Geometric means and coefficients of variation will be presented for C_{max} , AUC, $t_{1/2}$, Cl, and V_d . Median, minimum, and maximum will be presented for T_{max} .

To describe the dependency on dose, scatter plots of C_{max} and AUC versus dose will be provided. Summary statistics will be tabulated for the trough (C_{min}) concentration and peak concentrations (end of infusion) by dose and study day. To assess the attainment of steady state, geometric mean C_{min} values will be plotted versus study day by dose.

Pharmacometric methods may also be applied to further investigate OBI-888 exposure (e.g., accumulation of OBI-888, presence of dose- or time-dependent OBI-888 PK behavior, verification of influential factors on OBI-888 PK).

Based on the PK data (PK profile of first dose, steady-state trough serum concentrations, C_{trough} , or $C_{min,ss}$) and targeted concentration (IC₅₀ in xenograft model), a PK modeling will be carried out for various dose regimens including 15 mg/kg weekly, 15 mg/kg every 2 weeks, or 15 mg/kg q3 weeks. Simulated C_{trough} of desired regimen should be above the targeted serum concentration. The steady-state trough serum concentrations should be above 2.4 ug/mL, from the preclinical xenograft model exhibiting IC₅₀ (trough level at 50% tumor inhibition) of 2.4 ug/mL.

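### As written, the Vss formula in SAP Appendix III has no infusion-time term and does not say which AUMC it uses; both need fixing, and the effect is minor

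*SAP*

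**What the plan says.** **The formula.** SAP Appendix III, section 3.4 lists Vss as "Volume of distribution at steady-state following iv administration" and computes it as total dose × AUMC / (AUC∞)². The same section defines two first-moment areas: one to the last quantifiable time, and one described as "Area under the first moment of the concentration-time curve from time zero to infinite time". The AUMC in the Vss formula carries no subscript. CL, "Total body clearance following iv administration", is dose / AUC∞, and Vz is CL / λ.

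**The dosing.** Appendix III, section 2.2 says the drug is "administered as a 90-minute intravenous (IV) infusion on Days 1, 8, 15, and 22 of each 28-day cycle". Protocol section 8.2.3 allows 10 minutes either way in Cycles 1 and 2. Shorter infusions are possible only from Cycle 3. Protocol section 14.4 says "PK parameters will be calculated using a non-compartmental method from the PK samples collected on Dose 1", so they do not enter this calculation.

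**The clock.** Appendix III, section 3.3 states that "nominal time is defined as the time in h since the start time of the dose". PK Table 2 has its first post-dose column at 1.5 h, the nominal end of infusion.

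**The software and outputs.** The WinNonlin settings in section 3.4 give the route as intravenous and mention no infusion duration. PK Listing 2 has columns for the start and end of each infusion. Vss is a column in PK Table 3 and PK Listing 5.

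**The concern.** Since CL = dose / AUC∞, the printed expression is CL × AUMC / AUC∞. That ratio is the mean residence time of drug in the body only when the whole dose enters at time zero. When the clock starts at the beginning of an infusion, the ratio also contains the average time the dose spends waiting to be infused. Nothing in the plan subtracts that time or defines a mean residence time.

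The unsubscripted AUMC is a second gap in the same line. Two analysts who follow the plan could choose different areas and report different volumes for the same patient.

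What is at stake is the accuracy and reproducibility of one reported PK parameter. The protocol's own PK list in section 14.4 names a volume of distribution but not Vss. The power model for dose proportionality uses only AUC and Cmax. No dose, stopping or efficacy decision rests on Vss.

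**Working it through.** The documents give no Vss value, so there is no stated figure to reproduce. The check is on the formula and the size of its error.

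**Inputs**
- Half-life 30 h and mean Vz 4.4 to 5.7 L across dose groups (protocol section 4.3.1).
- Cmax/D 0.246 to 0.275 (same section). Units are assumed to be µg/mL per mg, as in PK Table 3.
- T = 1.5 h nominal, 80 to 100 minutes permitted.
- Last Dose 1 sample at 169.5 h (PK Table 2).

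**1. Algebra.** For a constant-rate infusion of length T timed from its start, AUMC∞/AUC∞ = MRT + T/2. Hence dose × AUMC∞ / (AUC∞)² = CL × (MRT + T/2) = Vss + CL × T/2.

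**2. Clearance.** CL = Vz × ln 2 / half-life. This gives 4.4 × 0.6931/30 = 0.102 L/h and 5.7 × 0.6931/30 = 0.132 L/h.

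**3. Infusion term, with AUMC∞.**
- Nominal: CL × 0.75 h = 0.076 to 0.099 L.
- Relative to a volume equal to Vz: 0.75 × 0.6931/30 = 1.7%.
- Over 80 to 100 minutes, T/2 is 0.67 to 0.83 h. The term is then 0.068 to 0.110 L, or 1.5% to 1.9% of Vz.
- If Vss is as low as 1/0.275 = 3.6 L, pairing it with the higher clearance gives 0.099/3.64 = 2.7%.

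**4. Numerical check.** Exact integration of a two-compartment model with a 1.5 h infusion and CL 0.1155 L/h gave a printed-formula excess of 0.08664 L. CL × 0.75 h is also 0.08664 L.

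**5. Simulated NCA at the scheduled times** (linear-up, log-down, one compartment, half-life 30 h; Part A and Part B times agree):

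| True Vss | Printed, AUMC∞ | After subtracting CL × T/2 | Printed, AUMClast |
|---|---|---|---|
| 4.400 L | 4.478 L (+1.8%) | 4.402 L | 4.040 L (−8.2%) |
| 5.700 L | 5.801 L (+1.8%) | 5.702 L | 5.233 L (−8.2%) |

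**6. Why AUMClast matters more.** Let x = 169.5 × 0.6931/30 = 3.916. The share of AUC beyond 169.5 h is e^(−x) = 2.0%, so such a profile easily passes the plan's 20% extrapolation limit. The share of AUMC beyond that time is e^(−x) × (1 + x) = 9.8%. Combined with the missing infusion term, 1.0177 × (1 − 0.098) = 0.918, which is 8.2% low. The two readings differ by 4.478 − 4.040 = 0.438 L, about 10% of the true 4.4 L.

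**7. A less tidy profile.** In an assumed two-compartment case (true Vss 4.740 L), simulated NCA with AUMC∞ gave 4.781 L at the Part A times and 4.762 L at the Part B times as printed. After correction it gave 4.695 L and 4.676 L. The infusion term is still 0.086 L, but sparse-sampling error of similar size runs the other way. With AUMClast, Vss was 8.8% to 9.1% low.

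**The case against.** **Too small to matter.** At about 1.7% the infusion term is small beside the plan's own tolerance of 20% extrapolated AUC. Part A had only 14 patients, and intensive Part B sampling covers the first 3 per cohort. Step 7 shows that other NCA error can be as large and of opposite sign. All of this stands and sets the severity. It does not make the formula right for an infused drug.

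**Every Vss is too high, always in the same direction.** A reader might infer this from the missing term. The documents do not support it, because the claim needs AUMC to mean AUMC∞, and the formula does not say so. Under AUMClast the error is larger and has the opposite sign. A subscript lost when the text was read from the PDF cannot be excluded, although the one on AUC∞ in the same formula survived. If the source shows AUMC∞, the ambiguity falls away and the infusion term remains.

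**The reported values are wrong.** This is also tempting and also not shown. The parameters come from WinNonlin, and the plan is silent on whether an infusion duration is entered. If it is entered and the software allows for it, the output would disagree with the plan's definition, and the definition would still need amending.

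**Subtracting T/2 is always enough.** It is not. Protocol section 8.3.1 allows an interrupted infusion to resume 30% to 50% slower. As an assumed example, give half the dose over 45 minutes, pause for 30 minutes, then give the rest over 90 minutes. T is 165 minutes and T/2 is 82.5 minutes, but the mean input time is 0.5 × 22.5 + 0.5 × 120 = 71.25 minutes. T/2 would over-correct by 11.25 minutes. The fix has to cover such cases.

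**Conclusion.** The point holds as a defect in the written definition, and it is minor. With AUMC∞ and the formula applied as printed, Vss is overstated by CL × T/2, about 0.08 to 0.10 L at the nominal 90 minutes. With AUMClast it would be about 8% too low, which makes the missing subscript the larger of the two gaps.

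The sizes rest on a 30 h half-life, clearance derived from mean Vz on a one-compartment approximation, and an uninterrupted constant-rate infusion. The direct term CL × T/2 does not depend on the number of compartments. The value of 0.75 h is nominal and not a figure for each patient. CL, Vz, half-life, AUC and Cmax, as defined in the plan, need no such correction.

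**What to change.** In SAP Appendix III, section 3.4:

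1. Replace the Vss line with Vss = CL × (AUMC∞/AUC∞ − MIT), where MIT is the mean input time, and print the ∞ subscript on both areas.
2. State that MIT = T/2 for an uninterrupted constant-rate infusion, with T the actual duration from the recorded start and end times.
3. State that, if the infusion was interrupted or its rate changed, MIT is calculated from the actual rate history, or the Vss is listed but flagged as not reliably calculated.
4. Add to the WinNonlin settings that the dose is entered as an infusion with its actual duration.

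The cost is a few lines of text. PK Listing 2 already carries the infusion start and end times. A rate history is needed only for interrupted or rate-changed infusions, and flagging is the fallback where it was not recorded.

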3.5. Descriptive Statistics

Subject-specific PK parameter estimates will be listed (PK Listing 5). PK estimates will be summarized in PK Table 3. Summary statistics will include mean, standard deviation (SD), minimum, maximum, median, coefficient of variation as a percent (CV%), GM, and geometric standard deviation (GSD)

4. LISTING OF PROPOSED TABLES, FIGURES, AND LISTINGS

PK Table 1: Summary of Demographic and Baseline Characteristics of Subjects Included in the PK Analysis Population

Parameter	PK Analysis Population (N=X)
Sex - N (%)	(N-X)
Male	
Female	
Age (years)	
Mean (SD)	
Median	
Min, Max	
Height (cm)	
Mean (SD)	
Median	
Min, Max	
Weight (kg)	
Mean (SD)	
Median	
Min, Max	
BMI (kg/m ₂)	
Mean (SD)	
Median	
Min, Max	
Race - N (%)	
American Indian or Alaska Native	
Asian	
Black or African American	
Native Hawaiian or other Pacific Islander	
White	

Statistical Analysis Plan: OBI-888-001 Review Status: Final Version: 2.0

Version Date: 02JUN2022

PK Table 2: Summary Statistics for Concentrations by Nominal Time

Subject ID	OBI-888 Concentration (μg/mL) by Nominal Time ¹ After Dose (h)									
	0	1.5	2.5	4.5	7.5	25.5	73.5	169.5		
UXX-001	Х	Х	Х	Х	Х	Х	Х	Х		
UXX-002	Х	х	Х	Х	Х	Х	Х	Х		
UXX-003	Х	Х	Х	Х	Х	Х	Х	Х		
	Х	Х	Х	Х	Х	Х	Х	Х		
Statistics										
N ₂	Х	Х	Х	Х	Х	Х	Х	Х		
Mean	X.X	X.X	X.X	X.X	X.X	X.X	x.x	X.X		
SD	x.x	x.x	x.x	x.x	X.X	x.x	x.x	x.x		
GM	X.X	X.X	X.X	X.X	X.X	X.X	x.x	X.X		
(Min, Max)	(x, x)	(x, x)	(x, x)	(x, x)	(x, x)	(x, x)	(x, x)	(x, x)		

¹ Times are relative to time of dosing.

² Number of data points used to compute the summary statistics. For calculation of summary statistics, BQL values were imputed as 0 if they did not come after a PK sample concentration that is above the LLOQ and treated as missing otherwise.

Review Status: Final Version: 2.0

Version Date: 02JUN2022

PK Table 3: Summary Statistics for PK Parameters

Statistic	T _{max} (h)	C _{max} (µg/mL)	C _{max_D} (µg/mL/mg)	AUC _(0-last) (h×μg/mL)	AUC _(0-last) _D (h×μg/mL/mg)	CL (L/h)	K _e (1/h)	t _{1/2} (h)	Vss (L)
N									
Mean									
SD									
Min									
Median									
Max									
CV %									
GM									
GSD									

[figure not shown]
Review Status: Final Version: 2.0

Version Date: 02JUN2022

[figure not shown]
APPENDIX 1. LIST OF PROPOSED PK FIGURES LIST OF PK FIGURES

PK Figure 1: Concentration Profiles for All Subjects by Time	15
PK Figure 2: Semi-log Concentration Profiles for All Subjects by Time	
PK Figure 3: Mean Concentration by Nominal Time	17
PK Figure 4: Mean Concentration by Nominal Time (Semi-Log)	

[figure not shown]
PK Figure 1: Concentration Profiles for All Subjects by Time

[figure not shown]
PK Figure 2: Semi-log Concentration Profiles for All Subjects by Time

PK Figure 3: Mean Concentration by Nominal Time

PK Figure 4: Mean Concentration by Nominal Time (Semi-Log)

Review Status: Final Version: 2.0

Version Date: 02JUN2022

